Patients will be enrolled into the trial upon providing informed consent. Each subject will be randomized after meeting the Eligibility Criteria and completion of baseline testing. Due to time required for baseline testing and scheduling of implant, sites will manage these items within the 30 day window as suited for the individual institution and patient. Procedures related directly to the study must not be performed prior to informed consent. Data collection will be noted prior to implantation of the device and at six months following implant, then long term at 12 and 18 months followed by annually post-implant for five years. Serious adverse events (SAE) will be collected throughout the study until study closure and will be adjudicated by an independent Clinical Event Committee (CEC).

Progress reports of the clinical outcomes will be reviewed by the DSMB after randomization of forty (40) patients and at least twice annually based on study progress. A progress report will be sent to FDA for review as specified in the Statistical Methods and Data Analysis section.

The total duration of the study including the enrollment and 12 month follow-up is expected to be approximately 36-42 months.

OBJECTIVES

Primary Objectives

The primary objectives of the study are to demonstrate the safety and efficacy of the C-Pulse therapy as compared to OMT. Refer to the section on Statistical Methods and Data Analysis for a detailed discussion of the definitions and methodology.

1. Primary Efficacy Objective:

To demonstrate the superiority of the C-Pulse therapy in increasing survival free from worsening heart failure resulting in hospitalization, LVAD implantation, cardiac transplantation or death as compared to OMT.

2. Primary Safety Objective:

To demonstrate the safety of the C-Pulse System by evaluating freedom from serious adverse events that are adjudicated as definitely related to device, therapy or procedure and resulting in either surgical intervention or death.

Secondary Objectives

The secondary objectives are as follows:

1. To demonstrate the superiority of C-Pulse therapy as compared to the OMT Control in improvement in 6 Minute Hall Walk score at 12 months post-randomization.
2. To demonstrate the superiority of C-Pulse therapy as compared to the OMT Control in improvement in 6 Minute Hall Walk score at 18 months post-randomization.

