Report all associated adverse events. Update the device tracking records with all products. If the device is not returned to Sunshine Heart Inc., justification must be provided in the log.

Subject Withdrawal and Study Exit

A Study Exit record shall be completed if subject is unable to or refuses to continue participation in the study. Notify the Sunshine Heart clinical support team as soon as possible upon learning of a subject withdrawal/study exit.

If the subject fails to comply with follow-up visits, the study center must make repeated attempts to contact the subject. Each attempt to contact the subject must be documented in the subject's records and in the database.

If the subject officially withdraws from the study, the investigator will document the reason for withdrawal and indicate any relationship of the withdrawal to the study or the device on the eCRF.

If a subject withdraws from the study at any time, there will be no penalty or loss of future medical care.

STATISTICAL METHODS AND DATA ANALYSIS

Analysis Population

All randomized subjects will be included in the evaluation of the primary efficacy objective. Subjects will not be allowed to cross-over. All subjects implanted with the C-Pulse System will be included in the evaluation of the primary safety objective. In the event a randomized subject does not receive the implant or does not receive the randomized therapy, the subject will be analyzed according to the randomized assignment for the primary analyses. Additional supporting analyses of the primary efficacy endpoint will be conducted (as treated and per-protocol) which exclude subjects who do not receive the randomized treatment or those with major protocol deviations. The defined analysis cohorts are:

- Intent to treat: All randomized subject irrespective of treatment actually received (primary efficacy analysis)
- As treated: All randomized subjects receiving treatment as randomized
- Per protocol: All randomized subjects without major protocol deviations

Primary Efficacy Endpoint

The primary efficacy endpoint is defined as freedom from worsening heart failure related hospitalization, LVAD implant, heart transplant, and death.

The primary efficacy endpoint includes all occurrences of worsening heart failure events and will be analyzed utilizing a multiple failure time analysis.

Hypotheses

H_0 : HR=1,

H_A : HR \neq 1,

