where HR is the hazard ratio; the ratio of the C-Pulse treatment group worsening heart failure event hazard relative to the Control group worsening heart failure event hazard. This is designed to demonstrate that C-Pulse[®] therapy increases the freedom from worsening heart failure events as compared to Control as evidenced by a HR that is less than 1 and the upper bound of the two-sided 95% confidence interval for the HR excludes 1. All occurrences of worsening heart failure events will be included in the primary endpoint analysis. Details of the analysis methods can be found in the Statistical Analysis Plan.

Primary Efficacy Endpoint Sample Size

Sample size was estimated using SAS v9.2 software under two sided test for a difference in freedom from worsening heart failure. For the purposes of sample size estimation, a time to first event analysis was used to provide a conservative estimate of the required number of events and subjects. The minimum required sample size and total number of worsening heart failure events was calculated under the following assumptions:

- Significance level = 0.05
- Power = 0.80
- Proportion for 6 month freedom from worsening heart failure event in Control group = 0.72
- Underlying treatment effect on the hazard ratio scale: HR = 0.70
- Accrual time of 2.5 years
- Minimum follow-up of 12 months
- 10% Attrition per year
- 1:1 allocation ratio

Under the above assumptions a total of 265 subjects with at least one worsening heart failure events are required to be observed to ensure adequate power which indicates a total of 388 subjects randomized. As the primary analysis will include all worsening heart failure events in a multiple event analysis, the power for the detection of a difference in freedom from worsening heart failure event may be greater than 80%.

Justification for Primary Efficacy Endpoint Sample Size Assumptions

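### The primary objective and conclusion are worded as event-free survival, but the test covers all occurrences, so a benefit confined to repeat events could be reported as increased freedom from events

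*Combined protocol and SAP*

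**What the plan says.** Under Objectives, the primary efficacy objective is "To demonstrate the superiority of the C-Pulse therapy in increasing survival free from worsening heart failure resulting in hospitalization", LVAD implantation, transplantation or death. Under Statistical Methods and Data Analysis, Primary Efficacy Endpoint, the endpoint is again defined as freedom from that composite. The next sentence changes the quantity: "The primary efficacy endpoint includes all occurrences of worsening heart failure events and will be analyzed utilizing a multiple failure time analysis".

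The Hypotheses paragraph tests HR = 1, where HR is the ratio of worsening heart failure event hazards. It reads success as showing that the therapy "increases the freedom from worsening heart failure events as compared to Control as evidenced by a HR that is less than 1", with the upper 95% limit also excluding 1. The Interim Analysis uses recurrent events too, and its efficacy threshold can lead to a recommendation to stop.

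On size, the protocol says that "a time to first event analysis was used to provide a conservative estimate of the required number of events and subjects", and adds that power with all events may exceed 80%.

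Additional Supportive Analyses, item 1, gives by arm the proportion of subjects with each component, a Kaplan-Meier curve for each, and the hospitalization rate per patient-year. The multiple-failure-time model is not named. Details are left to a separate Statistical Analysis Plan whose text was not supplied.

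**The concern.** Event-free survival is settled at the first event; a second hospitalization cannot change it. An HR over all occurrences mixes first and later events. If the device acts differently on first and repeat events, one null can be true while the other is false.

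The documents give some reason not to take a constant effect for granted. Treated subjects have thoracic surgery on Day 0, and Potential Risks lists worsening heart failure among the risks of the procedure. System Features expects benefit through remodeling with chronic use. These points concern time rather than event order, but they leave room for the two effects to differ.

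At stake is what a trial meant to support marketing approval may say. Fewer readmissions among subjects who have already had an event is a real benefit, but it is not longer event-free survival.

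**Working it through.** **Inputs from Primary Efficacy Endpoint Sample Size.** The control rate is given as "Proportion for 6 month freedom from worsening heart failure event in Control group = 0.72". The other inputs are a design HR of 0.70, two-sided alpha 0.05, 80% power, recruitment over 2.5 years, at least 12 months on study, 10% attrition a year, equal arms and 388 subjects in all.

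**1. The plan's own figure.** Schoenfeld events: 4(1.960 + 0.842)² / (ln 0.70)² = 4 × 7.849 / 0.1272 ≈ 247.

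- Control hazard: −ln(0.72)/0.5 = 0.657 per year. Treatment hazard: 0.70 × 0.657 = 0.460.
- Loss hazard: −ln(0.9) = 0.105 per year.
- With uniform accrual and 1 to 3.5 years of follow-up, the chance of an observed first event is 0.682 (control) and 0.566 (treatment), mean 0.624.
- N = 247/0.624 ≈ 396, within 3% of 388.
- At 388, expected first events are 388 × 0.624 ≈ 242, and power is Φ(√242 × 0.3567/2 − 1.960) = Φ(0.814) ≈ 0.79.

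So 388 subjects and 80% power reproduce, as a first-event design. (The stated 265 events is not the required count on this formula; that is a separate matter.)

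**2. Assumptions the documents do not give.** These are the repeat-event rate as a multiple of the first-event rate, the share of events that are terminal, the repeat-event HR, frailty, and the model. Simulations used N = 388 with the accrual, follow-up and attrition above and 1,000 to 10,000 trials per scenario. They compared a robust all-events Cox-type (Andersen-Gill) test with a first-event test. Success was significance in favor of treatment at two-sided 0.05.

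**3. Effect only after the first event (first-event HR 1.00, no frailty).**

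| Repeat rate | Terminal share | Repeat HR | All-events success |
|---|---|---|---|
| ×1 | 30% | 0.70 | 20% |
| ×2 | 30% | 0.70 | 30-31% |
| ×2 | 25% | 0.70 | 37% |
| ×2 | 15% | 0.70 | 46% |
| ×1 | 25% | 0.50 | 59% |
| ×2 | 30% | 0.50 | 76-77% |
| ×2 | 25% | 0.50 | 84% |

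The lowest value seen was 19%. The first-event test stayed at 2-3%. At ×2 and 25% terminal, the mean all-events HR was 0.85 (repeat HR 0.70) or 0.75 (repeat HR 0.50), with a mean first-event HR of 1.00. In the 25% terminal runs the repeat effect applied to every later event, including terminal ones.

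Sensitivity: gamma frailty of variance 1 (25% terminal, ×1-3) lowers success to 16-23% at repeat HR 0.70 and 44-66% at 0.50. At ×2 without frailty, moving the terminal share from 10% to 50% takes success from 54% to 16% and from 96% to 44%.

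**4. No effect on any event.** The all-events test succeeded in 2.4% of trials and the first-event test in 2.6%, against 2.5% nominal.

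**5. Power with first-event HR 0.70 (×2, 25% terminal).**

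| Repeat HR | All-events / first-event, no frailty | All-events / first-event, frailty variance 1 |
|---|---|---|
| 0.70 | 96% / 79-80% | 62% / 46% |
| 0.80 | 89% / 80% | 47% / 46% |
| 0.90 | 77% / 80% | 32% / 43% |
| 1.00 | 62% / 79% | 21% / 44% |

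Break-even is near a repeat HR of 0.88, or 0.80 with frailty. With frailty, a conditional HR of 0.70 is a marginal first-event HR of about 0.77, so both tests have less power. Across ×1-2 and 15-30% terminal without frailty, power at repeat HR 1.0 was 62-64%, against 78-81% for the first-event test.

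**The case against.** The recurrent-event analysis is openly pre-specified in the endpoint, hypothesis and interim sections, and HR is defined as an event hazard ratio. Total heart failure events are a legitimate measure of burden, and the analysis gains power if the effect persists. All of this stands, and it is why the all-events test should remain primary.

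Four stronger readings are tempting and should not be drawn:

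- **Inflated type I error.** A reader might set 19-76% against 2.5%. But when the repeat HR is below 1, the null on all occurrences is false and those rejections are correct. What is unsupported is the freedom-from wording attached to them.
- **A general loss of power for delayed first events.** Power falls only if the effect largely disappears after the first event. The protocol's statement that power may exceed 80% is hedged and fits a persistent effect.
- **First-event sizing is conservative only if repeat events respond at least as strongly.** This is false: at repeat HR 0.80, all-events power was 84-91% without frailty, against 79-80% for the first-event test.
- **Nothing planned would reveal the pattern.** Setting the proportion hospitalized and the component curves against the hospitalization rate per patient-year gives a partial, descriptive answer.

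The separate Statistical Analysis Plan may contain a first-event analysis. That cannot be excluded, but it would not by itself correct the wording of the objective, endpoint and conclusion.

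**Conclusion.** The point holds as a mismatch between claim and test. The protocol would read an all-occurrences HR below 1 as increased freedom from events, which that HR does not establish. With identical first-event hazards, the rule succeeded in about 19-76% of trials at repeat HR 0.5-0.7, under repeat rates of one to two times the first-event rate, 15-30% terminal events, no frailty and a robust all-events Cox-type model. The upper figure is not a ceiling, since one run inside those ranges gave 84%; frailty or a larger terminal share lowers the figures. Another multiple-failure-time model would weight first events differently, so the percentages illustrate the size rather than predict it.

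Type I error for the stated null is nominal. The power cost is conditional: about 62-64% if the effect vanishes after the first event, and above 90% without frailty if HR 0.70 persists. The supplied text contains no comparison of time to first composite event between arms.

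**What to change.** - Keep the all-events analysis as primary.
- Reword the primary efficacy objective (Objectives), the endpoint definition (Primary Efficacy Endpoint) and the conclusion (Hypotheses) as a reduction in the total rate of worsening heart failure hospitalization, LVAD implant, transplant and death. The Design section carries similar wording and should follow.
- Pre-specify time to first composite event in all randomized subjects, with a Cox HR, 95% CI and Kaplan-Meier curve, as the first supportive analysis. Base any statement about freedom from events or event-free survival on it.
- Optionally, say in the sample size section that first-event sizing is conservative provided the treatment effect does not largely fade after the first event.

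The cost is wording plus one analysis of data already collected, with no added subjects. The downside is that a freedom-from claim would then depend on a second, supportive result with about 79% power at HR 0.70.

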¹³ PMA P100047: FDA Summary of Safety and Effectiveness Data HeartWare® Ventricular Assist System : Left Ventricular Assist Device.

¹⁴ PMA P060040/S5: FDA Summary of Safety and Effectiveness Data Thoratec HeartMate® 11 Left Ventricular Assist System (LVAS).

- Summary of baseline demographic, medical history and heart failure related assessments
- Summary of all available follow-up assessments

The initial enrollment period for the IDE study is intended to provide a period of review for safety to ensure that the risk/benefit assessment has not worsened and that the product/procedural/training enhancements have indeed provided the potential for improvement in outcomes such as exit site infections. Specifically, if more than 8 of 20 implanted subjects experience an exit site infection per the protocol definition, within six months of device implant, the enrollment will be halted until a resolution is agreed upon with FDA, the clinical advisors and Sunshine Heart Inc. A stopping rule will also be followed in the event more than 7 of 20 implanted subjects die during device support within twelve months of device implant and the mortality event is adjudicated as possibly or definitely related to the procedure, therapy or device. The company will halt enrollment while FDA, the clinical advisors and Sunshine Heart Inc. come to a resolution on continuing the trial.

Since this interim analysis is only for the purposes of safety and there is no potential for early stopping for efficacy, there is no type I error inflation and no adjustment required to the primary analysis of the protocol.

Interim Analysis

An interim analysis will be conducted when approximately 194 randomized subjects have been followed to twelve months. The interim analysis will evaluate the primary endpoint of a comparison of worsening heart failure events using all accrued, fully adjudicated primary endpoint events of recurrent worsening heart failure. The results of the interim analysis will be evaluated by the DSMB against a futility stopping rule for a finding of efficacy on the primary objective. Details of the analysis methods can be found in the Statistical Analysis Plan.

Additionally, an assessment of early efficacy will be made. The interim analysis will have a significance cutoff for superiority. At the interim analysis, the DSMB may make one of the following recommendations:

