1. If the test statistic for the primary endpoint crosses the futility threshold, the DSMB may recommend that enrollment be discontinued for futility.
2. If the test statistic for the primary endpoint crosses the efficacy threshold the DSMB may make one of the following recommendations:
 - A. recommend that the trial be stopped for efficacy
 - B. recommend that the control arm be dropped as the enrollment of the treatment arm continues in order to achieve a minimum of 12 months of follow-up on a defined number of implanted subjects
 - C. recommend that the trial continues as planned to obtain a better precision on the treatment effect.
3. If neither the futility nor the efficacy boundaries are crossed, the DSMB may recommend that trial enrollment and follow-up continue as planned.

Secondary Efficacy Endpoints

The following secondary endpoints will be analyzed according to the objectives and hypothesis tests given below. Testing of the hypothesis driven secondary efficacy objectives will be conducted only in the event the primary efficacy objective and primary safety objectives are met, thereby preserving an overall Type I error rate of 5%. The secondary efficacy endpoints and associated analyses are described below:

1. Improvement in 6 Minute Hall Walk at 12 months

The improvement in 6 Minute Hall Walk will be computed as the difference between the baseline and follow-up value at 12 months. Subjects not evaluated at 12 months due to prior VAD implant, heart transplant or death will have the worst possible outcome imputed for improvement. Subjects unable to perform the 6MHW will have a value of 0 for the 12 month result. Improvement at 12 months will be compared between treatment groups under the following hypotheses.

Hypotheses

$$H_0: DT = D_c$$

$$H_A: DT \neq D_c,$$

where DT represents the distribution of improvement in 6MHW for the Treatment and D_c the distribution of improvement in 6MHW for Control. Details of the analysis methods can be found in the Statistical Analysis Plan.

2. Improvement in 6 Minute Hall Walk at 18 months

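### As written, the final efficacy rule is an unadjusted two-sided 95% confidence interval although an interim look can stop the trial for efficacy, and no interim boundary or matching final level is stated

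*Combined protocol and SAP*

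**What the plan says.** **Final rule.** Under Primary Efficacy Endpoint, Hypotheses, the trial succeeds if the hazard ratio is below 1 and "the upper bound of the two-sided 95% confidence interval for the HR excludes 1". This is a nominal two-sided 0.05 test.

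**Sizing.** Primary Efficacy Endpoint Sample Size lists "Significance level = 0.05" with 80% power. No interim look appears among the assumptions.

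**Interim.** The Interim Analysis section plans one look at the primary endpoint when about 194 randomized subjects have 12 months of follow-up. Besides futility it provides: "Additionally, an assessment of early efficacy will be made. The interim analysis will have a significance cutoff for superiority". If the threshold is crossed, the DSMB may recommend stopping for efficacy, dropping the control arm, or continuing.

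**What is deferred.** Both the hypotheses section and the interim section refer to a Statistical Analysis Plan for details of the methods. No interim boundary or adjusted final level appears in the available text.

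**Error claim.** The Secondary Efficacy Endpoints section makes secondary testing conditional on the primary objectives, "thereby preserving an overall Type I error rate of 5" percent. The section on type I error control for the secondary objectives repeats the claim. The only explicit statement that no adjustment is needed concerns the early safety report after 40 randomizations. Its reason is that that report cannot lead to early stopping for efficacy.

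**The concern.** A trial that can win at an interim look and again at the end has two chances of a false positive. If the final test keeps the full 0.05, the total exceeds 0.05 by whatever the interim adds. The protocol accepts this principle when it exempts the safety report, but it makes no allowance for the interim to which the principle applies.

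At stake is the primary success rule of a trial intended to support marketing approval. There is also a practical problem. If the SAP does set an adjusted final level, the protocol and the SAP would disagree on results just below 0.05. A final p of 0.0485 would succeed under the protocol's interval and fail against a level of 0.048. That should not be resolved after unblinded data exist.

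**Working it through.** **1. The plan's own figure.** The sizing section says "Sample size was estimated using SAS v9.2 software under two sided test for a difference in freedom from worsening heart failure". With HR 0.70, two-sided 0.05 and 80% power, the Schoenfeld count is 4 × (1.960 + 0.842)² / (ln 0.70)² = 4 × 7.849 / 0.1272 = 247. Freedman's formula gives 253. The plan states 265, so its count is not reproduced. It does not look like an allowance for an interim either: 388 × 0.685 = 266 is what 388 subjects would yield with no attrition. That mismatch is a separate matter. Here it matters only that the sizing is for a fixed design.

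**2. Information at the interim.** Inputs from the sample size section:
- a control-group event-free share of 0.72 at 6 months;
- a hazard ratio of 0.70, device against control;
- enrolment over 2.5 years, with every subject followed for at least one year;
- yearly attrition of 10%, and 388 subjects split equally between the arms.

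Assumptions added here: exponential times, uniform accrual, first events only.
- Control hazard: −ln(0.72)/0.5 = 0.657 per year. Device hazard: 0.70 × 0.657 = 0.460. Attrition hazard: −ln(0.90) = 0.105.
- The 194th subject enters at 2.5 × 194/388 = 1.25 years, so the interim falls at 2.25 years. The final analysis falls at 2.5 + 1 = 3.5 years.
- Expected first events per arm at time T, with λ = h + 0.105, m = min(T, 2.5) and 194/2.5 = 77.6 entries per year: 77.6 × (h/λ) × [m − (e^(−λ(T−m)) − e^(−λT))/λ].
- At 2.25 years: 78.5 + 61.7 = 140.2. At 3.5 years: 132.4 + 109.8 = 242.2.
- Information fraction t = 140.2/242.2 = 0.579. Against the plan's 265 events it would be 140.2/265 = 0.53.

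**3. Type I error with the final test left at 1.96.** Under the null the interim and final statistics are bivariate normal with correlation √0.579 = 0.761. A crossing at the interim counts as a positive result.
- Two-sided: 1 − P(|Z₁| < c₁, |Z₂| < 1.96).
- False claim of benefit: 1 − P(Z₁ < c₁, Z₂ < 1.96).

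The cutoffs below are assumptions, because the text gives none. The last column is the final nominal level that would restore 5% overall.

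| Interim cutoff (two-sided p) | Two-sided error | False benefit | Matching final level |
|---|---|---|---|
| 0.001 | 5.01% | 2.51% | 0.0499 |
| 0.0064 (Lan-DeMets, O'Brien-Fleming type) | 5.20% | 2.60% | 0.0479 |
| 0.0090 (classical O'Brien-Fleming) | 5.31% | 2.66% | 0.0467 |
| 0.0304 (Pocock) | 6.6% | 3.30% | 0.0304 |
| 0.05 | 8.0% | 4.02% | none left |

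**4. Sensitivity to the fraction.** With an interim p<0.05 the two-sided error is 8.6% at t = 0.4 and 7.6% at t = 0.7. With p<0.001 it is 5.04% and 5.004%. The total stays above 5% throughout.

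**5. Cost of adjusting.** At 265 events and HR 0.70, power is 0.827 with an unadjusted single final test. With Lan-DeMets O'Brien-Fleming-type spending at t = 0.579 it is about 0.824. With Pocock it is about 0.792.

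**The case against.** **The boundaries may be in the SAP.** This stands as a limit on the conclusion. A reader might infer that the 5% level is in fact lost. The documents do not support that, because the methods are deferred and the boundary text is not available. However, the protocol does not defer the success criterion; it states it. An SAP with an adjusted final level would contradict that statement, so the protocol wording needs to change in either case.

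**A false claim of benefit stays well below 5%.** Correct. Success requires the interval to lie below 1, so the nominal error in that direction is 2.5% and rises to 4.0% at most in the table. Only the two-sided figure passes 5%. The inflation is measured against 2.5%, and it remains.

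**The secondary claims.** A reader might infer that every gated secondary test then exceeds 5%. That does not follow: a looser gate does not raise the error of one test done once at its own 5% level. What the text leaves open is the level for the secondary hierarchy if efficacy is declared at the interim. Immediate testing then is not stated. The Secondary Efficacy Endpoints section also requires the primary safety objective, which needs at least 182 subjects, whereas about 97 of the 194 at the interim would be in the device arm.

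**The size may be trivial.** True for conservative cutoffs: 0.01 to 0.3 points. Nothing in the text shows that 0.05 would be used at both looks, and nothing rules out a Pocock-type cutoff.

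**Futility stopping could offset it.** A binding rule could. For example, O'Brien-Fleming-type spending at t = 0.5 with binding futility at z<0.5 gives a one-sided error of 0.0240. But the DSMB is only permitted to recommend stopping for futility, so no credit is due.

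**The fraction counts first events.** It does, while the analysis uses recurrent events. The true fraction is unknown and the decimals are illustrative; the direction does not change.

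**Conclusion.** The point holds for the rule as written. The protocol pairs a final test at the full two-sided 0.05 with an interim that can declare efficacy, and states no allocation of error between them. Taken literally, the two-sided type I error is above 5% for any non-zero interim cutoff: 5.01% to 8.0% over the cutoffs examined, and 5.2% to 5.3% for O'Brien-Fleming types. The chance of a false benefit claim is 2.51% to 4.0% against a nominal 2.5%.

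These figures assume exponential first-event times, uniform accrual, an information fraction of 0.58, non-binding futility, and that crossing the interim threshold counts as success. Actual inflation is not established, because the boundary is not in the available text. The matter should be settled before the interim, but it ranks below a mandatory correction unless the SAP cutoff turns out to be liberal, of Pocock type or looser.

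**What to change.** Before the interim:
- In the hypotheses section, replace the 95% interval rule with the final critical level that matches the interim boundary, and an adjusted interval of the same coverage. One suitable choice is O'Brien-Fleming-type Lan-DeMets spending evaluated at the observed information fraction, which leaves about 0.048 for the final test at 58%. Other boundaries would serve if stated in advance.
- State the interim cutoff and how information is measured for the recurrent-event analysis. Make the protocol and the SAP agree.
- State that futility is non-binding.
- Set the level for the secondary hierarchy if efficacy is declared at the interim.
- Say that the 80% power figure is for a fixed design.

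This takes about one paragraph in each document. With O'Brien-Fleming-type spending it costs about 0.3 points of power at 265 events (0.827 to 0.824). A Pocock boundary would cost about 3.5 points.
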